2.15.2 Sample Size Rationale

Based on the need for data collected from this study, it was determined that a total of 50 subjects will be required, including departures.

2.15.3 Patient Populations

Interim results may be collected and reported. All data will be analyzed at the end of the study. The primary analysis will be performed by the intention-to-treat approach. Everyone who begins the treatment is part of the study whether he or she completes the study or not. Additional per-protocol analysis may also be performed on subjects who complete the entire clinical trial according to the protocol. The most appropriate method of handling missing values will be chosen based on the individual trial goals, endpoints and context.

The analysis of demographic, medical history, and efficacy variables will be based on all patients who are randomized and receive at least one treatment. The analysis of safety data will be based on all patients who are randomized, receive at least one treatment, and have at least some safety data.

2.15.4 Analysis of Demographic and Medical History Variables

Summaries will be prepared for all important demographic and medical history variables. For quantitative variables summaries will include the sample size, mean, median, standard deviation, minimum, and maximum. For these variables the treatment groups will be compared using either a t-test or a Wilcoxon Rank Sum test, as appropriate. For categorical variables the summaries will include the sample size and the number and percent of patients for each outcome. For these variables the treatment groups will be compared using Fisher's Exact test. Statistical significance will be declared if the two-sided p-value is < 0.05 .

2.15.5 Analysis of Efficacy Variables

Additional efficacy variable is the change from baseline to Visit 7 (12 week follow up visit). Baseline is defined as the last assessment prior to the first treatment. The change from baseline to visits 6 and 7 will be analyzed using a Mixed Model Repeated Measures Analysis of Variance. A pairwise treatment group comparison at visit 7 will be performed using the results of this analysis. If a patient has no post-baseline assessment of the primary efficacy variable it will be assumed that the change from baseline to visit 7 is zero. The changes to visits 6 and 7 will be left as missing. Statistical significance with respect to the treatment group comparison at visit 7 will be declared if the two-sided p-value is < 0.05 . For each treatment group, summaries will be prepared for both the observed assessment and the change from baseline. The summaries will include the sample size, mean, median, standard deviation, minimum, and maximum. The statistical significance of the mean change from baseline for each treatment group will be determined using a paired t-test.

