2.0 PROTOCOL

2.1 Protocol Methodology and Analysis

Methodology:

Subjects are to be enrolled in this clinical study if they are a healthy male or female 18 years of age or older. Up to 50 subjects will be enrolled at 3 study centers. Subjects will be enrolled into 2

groups, Group A for TempSure treatments only and Group B for TempSure and Icon treatments. Randomization will not be required as subjects will only be enrolled in Group B and treated with the Icon device if they present with pigment and/r vascular lesions. Subjects will attend a screening/pre-treatment visit which may be performed on the same day as the treatment visit. Subjects in Group A will receive up to 4 treatments with the TempSure device on the face. Subjects in Group B will receive 2 treatments with just the TempSure device and 2 treatments with both the TempSure and Icon device. Some subjects may be asked to return for an optional 5th treatment (2 – 3 weeks post last treatment) with the Icon device (and/or TempSure device) after the completion of their 4 treatments at the discretion of the Investigator. Subjects may receive a phone call 1 week (1-7 days) after each treatment to record side effects. Subjects will return for follow up visits at 4 and 12 weeks post last treatment for efficacy and side effects assessments. An unscheduled visit or phone call may be performed at any time during the study at the request of the subject or as deemed necessary by the site Investigator.

Analysis:

Upcoming generations are proving to have an interest in non-ablative aesthetic treatments and will drive demand for innovated products, procedures, and practice design.¹ Due to this shift in patient base, practices need to evolve to adapt to the newer generational ideologies. There have been rapid advances in RF technology over the past few years and the nonsurgical treatment using this energy source offers great promise to our aging population.² Radiofrequency technology for the treatment facial wrinkles and skin laxity needs to be further investigated to optimize treatment parameters for safe and effective non-ablative aesthetic treatments.

Relevance:

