2.13 Evaluation Methods

Photographs:

Photographs will be taken at baseline and at the 4 and 12 week follow up visit, and may be taken at eat treatment visit to assess the efficacy and safety of treatment.

Treatment Discomfort/Pain Evaluation:

Subjects will be asked to report the general level of treatment discomfort on a scale of 0 (none) to 10 (maximum intolerable pain) using the universal pain assessment tool (Appendix B)

Fitzpatrick Wrinkle Severity Scale

The Fitzpatrick Wrinkle Severity Scale will be used to evaluate outcomes. Live evaluation will be performed at Baseline and the 4 and 12 week follow up visits. The results will be compared to determine improvement.

Class	Wrinkling	Score	Degree of Elastosis
I	Fine wrinkles	1-3	Mild (fine textural changes with subtly accentuated skin lines)
II	Fine to moderate-depth wrinkles, moderate number of lines	4-6	Moderate (distinct papular elastosis [individual papules with yellow translucency under direct lighting] and dyschromia)
III	Fine to deep wrinkles, numerous lines with or without redundant skin folds	7-9	Severe (multipapular and confluent elastosis [thickened yellow and pallid] approaching or consistent with cutis rhomboidalis)

Subject Treatment Questionnaire:

Subject treatment questionnaires may be collected from each subject to obtain feedback on their treatment experience.

Blinded Evaluation:

Three blinded independent reviewers will perform a photographic evaluation in which they will be asked to identify pre-treatment images when compared to post treatment images. The reviewers will be Board Certified Dermatologists and/or Surgeons and will be chosen based on availability and have relevant clinical experience. They will attend a training session prior to grading.

Physician and Subject Questionnaire:

The Global Aesthetic Improvement Scale (GAIS) ranging from “worse” to “very much improved” will be used to judge the improvement as seen by the subject and Investigator.

Global Aesthetic Improvement Scale Assessment	
Rating	Description
1	Very Much Improved- Optimal cosmetic result in this subject

2	Much Improved- Marked improvement in appearance from the initial condition, but not completely optimal for this subject.
3	Improved- Obvious improvement in appearance from initial condition, but a re-treatment is indicated.
4	No Change- The appearance is essentially the same as the original condition.
5	Worse- The appearance is worse than the original condition.

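### The visit 7 test of Group A against Group B comes from a mixed model with no covariates specified, although the groups are not randomised, so it may be confounded by baseline severity and site

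*Combined protocol and SAP*

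**What the plan says.** Section 2.15.5 describes an additional efficacy variable, change from baseline, without naming the scale. The model is given in one sentence: "The change from baseline to visits 6 and 7 will be analyzed using a Mixed Model Repeated Measures Analysis of Variance". Next comes the group test: "A pairwise treatment group comparison at visit 7 will be performed using the results of this analysis". It carries a formal rule: "Statistical significance with respect to the treatment group comparison at visit 7 will be declared if the two-sided p-value is < 0.05". No fixed effects, covariates, random effects or covariance structure are listed there or elsewhere.

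Section 2.1 explains how the groups arise: "Randomization will not be required as subjects will only be enrolled in Group B and treated with the Icon device if they present with" pigmented or vascular lesions. It also says "Up to 50 subjects will be enrolled at 3 study centers". Section 2.15.3 nevertheless defines the efficacy and safety sets by reference to randomised patients.

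The data needed for adjustment are collected. The schedule in 2.12 places FWSS at visits 1, 6 and 7, and 2.13 says "Live evaluation will be performed at Baseline and the 4 and 12 week follow up visits". Section 2.15.4 compares the groups on demographic and medical history variables, but nothing from that comparison feeds into the efficacy model.

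**The concern.** A contrast without covariates relies on the groups being comparable at the start, and this design does not provide that. The documents give some reason to expect differences:

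- **Baseline severity.** The FWSS class II description in 2.13 includes dyschromia, which overlaps with the pigmented lesions that lead into Group B. The eligibility criteria in 2.3 set no range of wrinkle severity. The compatibility paragraph of 2.1 links more severe disease to a need for more treatment to get the same response, so the sponsor itself treats severity as related to outcome.
- **Site.** Appendix A shows that site 3, the Icon device and the two groups came in with the same revision, so the group mix may differ by site. If FWSS is scored live, raters will probably differ by site as well.

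Section 2.1 says that the data are meant to support marketing claims. A p-value below 0.05 for Group A against Group B could be read as an added effect of the Icon device.

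**Working it through.** The plan has no figure to reproduce. On sample size, 2.15.2 says only "Based on the need for data collected from this study, it was determined that a total of 50 subjects will be required, including departures", with no effect size, SD, power or dropout rate.

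**Inputs from the documents:** up to 50 subjects, 3 sites, two-sided alpha 0.05.

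**Assumptions, shown as ranges:** one post-baseline visit; equal variances at baseline and follow-up; within-group correlation ρ from 0.3 to 0.9; baseline difference D (Group B minus Group A) of 0, 0.5 or 1 SD; group splits 25/25, 35/15 and 40/10.

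**1. What the contrast can detect.** With 80% power the detectable difference is (1.960 + 0.842) × √(1/nA + 1/nB):
- 25/25: 2.802 × 0.283 = 0.79 SD of change
- 35/15: 2.802 × 0.309 = 0.86 SD
- 40/10: 2.802 × 0.354 = 0.99 SD

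Power for a difference of 0.5 SD is 42%, 37% and 29% respectively.

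**2. How far adjustment moves the answer.** The change contrast is (difference at follow-up) − D. The baseline-adjusted contrast is (difference at follow-up) − ρD. They differ in expectation by −(1−ρ)D:
- D = 0: no difference
- ρ = 0.7, D = 0.5: −0.15 SD
- ρ = 0.5, D = 0.5: −0.25 SD
- ρ = 0.3, D = 1: −0.70 SD

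**3. Effect on the error rate if outcome depends on baseline.** At 25/25, ρ = 0.5 and D = 0.5, the SE of the change contrast is √(2 × 0.5 × 0.08) = 0.283. The shift is 0.25/0.283 = 0.88 SE. The two-sided error is 1 − Φ(1.96 − 0.88) + Φ(−1.96 − 0.88), about 14% instead of 5%. At ρ = 0.7 and D = 0.5 it is about 10.5%.

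**4. Which contrast is right depends on the true model.** A 20,000-run simulation at 25/25, ρ = 0.5, D = 0.5 gave:
- outcome driven by baseline: change contrast off by −0.25 SD, adjusted contrast by 0.00;
- stable group difference with parallel change: change contrast off by 0.00, adjusted contrast by +0.25 SD.

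**5. Precision.** The variance ratio, adjusted over unadjusted, is [(1+ρ)/2] × [1 + D²/((N−2)(1/nA + 1/nB))]. At 25/25 the second bracket is 1 + D²/(48 × 0.08) = 1 + D²/3.84.

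| D (SD) | ρ = 0.3 | ρ = 0.5 | ρ = 0.7 | ρ = 0.9 |
|---|---|---|---|---|
| 0 | 0.65 | 0.75 | 0.85 | 0.95 |
| 0.5 | 0.69 | 0.80 | 0.91 | 1.01 |
| 1 | 0.82 | 0.95 | 1.07 | 1.20 |

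**6. Site.** Adjusting for site multiplies the variance by [1/Σ(ab/(a+b))] / (1/nA + 1/nB), where a and b are the group sizes at each site, before any gain from removing variation between sites:
- A/B splits of 9/8, 8/9, 8/8: 1.00
- 12/5, 9/8, 4/12: (1/10.76)/0.08 = 1.16; site must explain 1 − 1/1.16 = 14% of the variance to break even
- 16/1, 8/9, 1/15: (1/6.11)/0.08 = 2.04; break-even is 51%

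**The case against.** The strongest reply is that 2.15.5 lists no model terms at all, so it has not ruled out baseline or site. That stands: the defect is a model left unspecified. A reader might infer that the plan deliberately excludes these covariates, but the text does not say so. It is also right that FWSS as the outcome is an inference from the schedule.

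A second reply is that bias has not been shown. That stands too. Group B is selected for lesions, not for a high wrinkle score. Dyschromia appears only in the class II description, and vascular lesions appear nowhere in the scale. Regression of both groups to a common mean therefore does not follow, and step 4 shows that baseline adjustment can itself mislead. Prescribing only the adjusted model would be hard to defend.

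A third reply is that bias and loss of precision cannot both be claimed at full size. The ratio (1+ρ)/2 holds only when baselines are equal, whereas the bias needs them to differ. At D = 1 SD the gain shrinks and reverses by ρ = 0.7. Site adjustment can also cost precision.

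Last, this is a secondary contrast. The primary endpoint in 1.2 is identification of pre-treatment photographs, and 1.2 lists no comparison between groups. This limits the importance of the point but does not remove it, because 2.15.5 attaches a significance rule to the contrast. The dependence on the model in step 4 is itself a reason to fix the terms before data are seen.

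**Conclusion.** The point holds as a risk in a secondary analysis. A formal p<0.05 test between non-randomised groups is planned with no covariates specified, although baseline FWSS and site are available. The contrast may be confounded by either, and it may lose precision.

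Under the assumed ranges, the bias if outcome depends on baseline runs from zero (D = 0) to 0.70 SD (ρ = 0.3, D = 1). The variance ratio from baseline adjustment runs from 0.65 to 1.20 at 25/25. Neither ρ, D, the SD nor the group sizes are in the documents, so these figures show scale and are not estimates for this trial.

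A reader might infer that the contrast is biased and that adjustment would correct it. The documents support neither. No imbalance is reported, and the adjusted contrast is the unbiased one only under some models. Adjustment for baseline and site would also leave two things confounded with group: lesion status, which defines the groups, and the optional fifth treatment, which 2.7 and the footnote in 2.12 assign to Group B only. The contrast cannot be read as an Icon effect under any of these models.

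**What to change.** In 2.15.5:

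- Name FWSS as the outcome, and say whether the live scores (2.13) or the photographic grades (1.2) are meant.
- Fit change at visits 6 and 7 on group, visit, group-by-visit and baseline FWSS, with an unstructured within-subject covariance. Add site if group and site are not nearly aliased, and set in advance how that will be judged.
- Report the visit 7 contrast with and without baseline adjustment.
- Label it an exploratory, non-randomised association that does not isolate an Icon effect, and give the two reasons: lesion status and the optional fifth treatment.

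The cost is a few sentences and no new data. The model uses one more degree of freedom for baseline and two for the three sites. Precision may fall if the groups are unbalanced on baseline or site, as steps 5 and 6 show. The label is also less favourable than a bare significance statement.

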1.2 Objectives

1. Primary Objective:
 - Photographic evaluation with correct identification of pre-treatment 2D images when compared to the 12 week follow up images performed by three independent reviewers.
2. Assessments:
 - Photographic evaluation with correct identification of pre-treatment 2D images when compared to the 4 week follow up images performed by three independent reviewers.
 - Photographic evaluation with Fitzpatrick Wrinkle Severity Scale (FWSS) grading comparing pre-treatment images to the 4 and 12 week follow up images performed by three independent reviewers.
 - Principle Investigator assessment using the Global Aesthetic Improvement Scale (GAIS) at the 4 and 12 week follow up visit.
 - Subject assessment using the Global Aesthetic Improvement Scale (SGAIS) at the 4 and 12 week follow up visit.
 - Subject Questionnaires
 - Pre-Treatment 1
 - Post Treatment 1
 - Follow Up
3. Safety Objectives:
 - Collection of Adverse Events
 - Collection of Treatment Discomfort/Pain Evaluation

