2.12 Schedule of Visits and Procedures

	Visit #1*	Visit #2 - 5	Treatment Visit*** (Optional)	Call (Optional)	Visit #6	Visit #7
Procedure	Screening and Pretreatment Procedures	Treatment Visits 1-4 (1 - 2 weeks apart)	Treatment Visit #5 (2 - 3 weeks post last treatment)	Phone Call 1 Week Post Each Tx (1-7 Days)	Follow Up 4 Weeks Post Last Tx (+/- 1 Week)	Follow Up 12 Weeks Post Last Tx (+/- 1 Week)
Medical History	X					
Pregnancy Verification**	X	X	X			
Informed Consent	X					
Photographs	X	X	X		X	X
FWSS	X				X	X
Subject Pre-Treatment 1 Questionnaire		X				
Treatment		X	X			
Treatment Discomfort/ Pain Evaluation		X	X			
Subject Post Treatment 1 Questionnaire		X				
PGAIS					X	X
SGAIS					X	X
Subject Follow Up Questionnaire					X	X
Adverse Events Assessment	X	X	X	X	X	X

*Screening and Pretreatment Procedures may occur at the same time as the first Treatment Visit.

**Pregnancy verification required before each treatment only for women of childbearing potential.

***Group B only

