2.15 Statistical Analysis**2.15.1 Hypothesis**

For this study to be considered a success, of pre-treatment images when compared to post treatment (90 day) images will be $\geq 80\%$.

For the additional assessments to be considered a success, the following must be true:

- In cases where the subject's improvement is being graded on a scale, such as the FWSS and GAIS scale, we will test the statistical significance of our results against a hypothetical population that would have no change (average score of 4).
- Subject treatment and clinician usability questionnaires are collected.
- The side effect profile (adverse events) and the average pain score is acceptable to the Physician as it relates to the type of treatment.

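### Section 2.15.5 gives two unreconciled instructions (zero and missing) for a subject with no post-baseline assessment, and attaches them to a primary endpoint that has no change score

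*Combined protocol and SAP*

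**What the plan says.** Section 2.15.5 (Analysis of Efficacy Variables) opens with "Additional efficacy variable is the change from baseline to Visit 7 (12 week follow up visit"). It analyses changes to visits 6 and 7 with a repeated-measures mixed model, compares the treatment groups at visit 7 at two-sided 0.05, and tests each group's mean change with a paired t-test. It does not name the scale.

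For a patient with "no post-baseline assessment of the primary efficacy variable it will be assumed that the change from baseline to visit 7 is zero". The sentence that follows is "The changes to visits 6 and 7 will be left as missing".

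The primary objective in section 1.2 is "Photographic evaluation with correct identification of pre-treatment 2D images when compared to the 12 week follow up images performed by three independent reviewers". Section 2.15.1 sets the criterion: "For this study to be considered a success, of pre-treatment images when compared to post treatment (90 day) images will be" at least 80%.

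On the FWSS, section 2.13 says "Live evaluation will be performed at Baseline and the 4 and 12 week follow up visits", whereas section 1.2 describes FWSS grading of photographs by three independent reviewers. The schedule in section 2.12 puts the FWSS at visits 1, 6 and 7, and both GAIS ratings at visits 6 and 7 only.

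Section 2.15.3 makes the primary analysis intention-to-treat: "Everyone who begins the treatment is part of the study whether he or she completes the study or not". It leaves the general method for missing values to be chosen later.

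**The concern.** Two programmers working from 2.15.5 could build different data sets. One would enter a visit 7 change of zero for every treated subject who never returned; the other would leave those subjects out of the visit 7 estimate. No phrase such as *otherwise* or *for other patients* separates the cases.

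The rule is also keyed to a variable that cannot have a change from baseline. An image pair is identified correctly or not, and there is no baseline value to subtract. Read literally, the rule has nothing to act on.

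At stake is the visit 7 comparison of Groups A and B. Filling with zeros pulls a group's mean change toward zero in proportion to the share of its subjects with no follow-up. If that share differs between groups, part of the reported difference comes from the filling and not from the treatments.

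**Working it through.** **1. Which variable can the rule apply to?**

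| Outcome | Before treatment | Visits 6 and 7 | Change score possible? |
|---|---|---|---|
| Image identification (primary) | image only, no score | identified or not | No |
| GAIS, investigator and subject | not scheduled | yes | No, the rating is itself a judgement of change |
| FWSS | yes | yes | Yes |

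Among the graded scales, only the FWSS fits.

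**2. Size of the shift.** The plan has no figure to reproduce: it states 50 subjects including departures, but no SD, effect size or dropout rate. All inputs below except the total of 50 and the 0.05 level are assumptions.

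Take a group of N treated subjects, k of them with no post-baseline assessment, and observed mean change m. Left missing, the mean is m. Zero-filled, it is m(N - k)/N, a shift of -mk/N. With m = -1.0 in both groups, so no true difference:

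- 5 of 25 missing in one group, none in the other: false difference 1.0 x 5/25 = 0.20 points.
- 5 of 20 missing in one group, none of 30 in the other: 1.0 x 5/20 = 0.25 points.
- 2 of 25 in each group: the shifts are equal and the false difference is 0.

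**3. False-positive rate at visit 7.** 100,000 simulated trials per case, normal changes, two-sample t-test, two-sided 0.05. Left missing, the rate is about 5% throughout. With zeros:

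| Group sizes | Missing | SD 1.5 | SD 1.0 |
|---|---|---|---|
| 25/25 | 0 v 5 | 7.4% | 10.0% |
| 30/20 | 0 v 5 | 8.1% | 12.6% |
| 25/25 and 30/20 | 0 v 2 | 5 to 6% | 5 to 6% |
| 25/25 | 2 v 2 | 4.5% | 4.1% |

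With a true change of -0.5, the 0 v 5 case gives 5.6% (25/25, SD 1.5) and 6.7% (30/20, SD 1.0). Simulation error is about 0.1 percentage point, since sqrt(0.1 x 0.9/100,000) = 0.00095.

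The t-test is a fair stand-in for the mixed model here. In 20 simulated data sets (30/20, 5 subjects with no follow-up, the rest complete, unstructured covariance, REML) the visit 7 t statistic agreed with the two-sample t to within 2e-7 under both rules.

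**4. One data set read two ways.** 25 per group, observed means 0.5 (A) and 1.0 (B) in points of improvement, SD 1.0. With 5 missing in A only, leaving them missing gives a difference of 0.50, p = 0.103. Zeros give A a mean of 0.5 x 20/25 = 0.40, a difference of 0.60, p = 0.031. With 5 missing in B only, zeros give 1.0 x 20/25 - 0.5 = 0.30, p = 0.289. The choice of rule can move the result across 0.05.

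**5. Within-group test.** 45 observed, mean -0.5, SD 1.5: t = -0.5/(1.5/sqrt(45)) = -2.236, p = 0.0305. Add 5 zeros: the mean is -0.5 x 45/50 = -0.45. The sum of squares is 44 x 2.25 + 45 x 0.05^2 + 5 x 0.45^2 = 100.125, so SD = sqrt(100.125/49) = 1.429. Then t = -0.45/(1.429/sqrt(50)) = -2.226, p = 0.0306. The mean shrinks by a tenth; the p-value does not move in any useful sense.

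**The case against.** The strongest reply is that the two sentences need not conflict. Zero may be meant for the summaries and paired t-test and missing for the mixed model, or the second sentence may concern subjects with some follow-up data. That stands as a possible intention, so a reader should not infer that the analysis is impossible to run. But the text adopts neither reading, and each gives a different data set.

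Second, the reference to the primary efficacy variable may be only a wrong label, because the section opens by calling the change an additional variable. That is largely right, and replacing the label repairs this half. The replacement still has to say which FWSS is meant, live or photographic.

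Third, the effect is small. The 7 to 13% rates need five subjects with no follow-up at all, every one in the same group. Sections 11.0 and 12.0 ask pregnant and withdrawing subjects for a final evaluation, which should make such subjects fewer. The comparison is of an additional variable between groups formed by lesion status, not by randomization, so equal true change is itself an assumption. All of this stands and limits the weight of the point.

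A reader might go further and infer that the 80% endpoint is compromised. The documents do not support that. Section 2.15.3 keeps everyone who begins treatment, so the denominator is largely stated, and a contrast that simply drops subjects without images would overstate the risk. What is open is narrower: how a treated subject without a 12-week image is scored.

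**Conclusion.** The point holds as a drafting conflict with a modest statistical consequence. Section 2.15.5 gives zero and missing for the same visit of the same subject without saying where each applies, and ties the rule to an endpoint with no change score.

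If zeros enter the visit 7 group comparison, the false-positive rate rises from 5% to about 7 to 13% with 0 against 5 missing and to 5 to 6% with 0 against 2. It falls slightly below 5% when missingness is equal. These figures assume equal true changes of -1.0, SD 1.0 to 1.5 and 50 subjects split 25/25 or 30/20; a smaller true change gives less inflation. Within-group p-values are essentially unaffected, and with no subject lacking follow-up the two rules agree.

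As a secondary matter, the rule cannot serve the 80% endpoint, so the score for a missing 12-week image remains a deferred choice. It should not be dismissed as irrelevant when few images are missing, because that depends on how the three reviewers' readings are combined. If they are pooled (3 x 50 = 150, threshold 120) and one subject is missing, scoring that subject's readings as not identified requires 120 correct of the other 147. Half credit, 1.5, requires 119.

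**What to change.** In 2.15.5:

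- Replace the two sentences with one rule: missing visits are left missing in the mixed model, and zero change for subjects with no post-baseline assessment is a sensitivity analysis.
- Replace the reference to the primary efficacy variable with the FWSS, and say whether it is the live evaluation of section 2.13 or the photographic grading of section 1.2.
- State that the summaries and paired t-test use observed changes.

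The cost is a few lines of wording and one sensitivity analysis, with no new data. The downside is that subjects who leave before visit 6 get no weight, so the mean change may be optimistic if they left for lack of effect; the zero-change analysis shows by how much. Keeping zero as the main rule for named analyses would also remove the ambiguity, but would keep the distortion whenever missingness is unequal and zeros enter the group comparison.

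Separately, and not needed to close this point: before any image is graded, fix how a treated subject without a 12-week image is scored for the 80% endpoint under intention-to-treat.

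### At visit 7 the within-group change is tested by a paired t-test on observed pairs, although the mixed model already planned in 2.15.5 would also use the week-4 scores of subjects who miss week 12

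*Combined protocol and SAP*

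**What the plan says.** Section 2.15.5 gives two methods for the same change score. The first is longitudinal: "The change from baseline to visits 6 and 7 will be analyzed using a Mixed Model Repeated Measures Analysis of Variance". Its one named use follows: "A pairwise treatment group comparison at visit 7 will be performed using the results of this analysis". The second is for change within a group: "The statistical significance of the mean change from baseline for each treatment group will be determined using a paired t-test". That sentence names no visit, no missing-data rule and no significance level. The 0.05 level in the section is tied to the group comparison: "Statistical significance with respect to the treatment group comparison at visit 7 will be declared if the two-sided p-value is < 0.05".

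Two adjacent sentences deal with missing values. One assigns a change of zero to subjects never assessed after baseline; it begins "If a patient has no post-baseline assessment of the primary efficacy variable it will be assumed that the change from baseline to visit 7 is". By contrast, the next sentence says "The changes to visits 6 and 7 will be left as missing".

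Section 2.15.3 states "The primary analysis will be performed by the intention-to-treat approach" and "Everyone who begins the treatment is part of the study whether he or she completes the study or not". It leaves the choice of missing-data method open.

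The variable in 2.15.5 is described only as an additional efficacy variable measured as change from baseline. In the schedule (2.12), the Fitzpatrick Wrinkle Severity Scale (FWSS) is the only efficacy scale scored at screening as well as at visits 6 and 7. The GAIS ratings have no baseline value. FWSS is therefore the natural reading.

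**The concern.** Take a subject with a baseline and a week-4 score who does not return at week 12. The zero-change rule does not apply, because this subject has a post-baseline assessment. The visit 7 change stays missing, so there is no pair to test at visit 7. The mixed model does use this subject's week-4 change. Whenever such subjects exist, the section therefore yields two different estimates of the same visit 7 group mean, and attaches the within-group p-value to the one that uses less of the data.

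Subjects who see little benefit at week 4 may have less reason to come back at week 12. If so, those who remain are a favourable selection, and the paired t-test overstates improvement at the visit that 2.15.5 treats as its efficacy time point. The study is open label and Group B is defined by presenting with lesions (2.1), so the A versus B contrast is hard to interpret. The within-group change is likely to be the result that readers look at, and 2.1 says the data are meant to support marketing claims.

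**Working it through.** **The plan's own figure.** Section 2.15.2 gives 50 subjects including departures, with no effect size, SD, power or dropout rate. There is nothing to reproduce, so the check concerns the method and its size rests on assumptions.

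**Inputs assumed (none is in the documents).** 25 subjects per group (2.1 fixes no split); SD of change 1 at each visit, so results are in SD units; correlation ρ between the visit 6 and visit 7 changes of 0.6 to 0.8; a proportion m of 10 to 20% missing visit 7; all of the missed visits from the worse half at visit 6. Improvement is counted as positive.

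**Step 1: selection at visit 6.** Let z be the standardised visit 6 change. If all missed visits come from z < 0, then E[z | seen at visit 7] = 0.798 × m / (1 − m), where 0.798 is the mean of |z| for a standard normal.
- m = 0.10: 0.798 × 0.10 / 0.90 = 0.089
- m = 0.20: 0.798 × 0.20 / 0.80 = 0.200

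**Step 2: bias of the observed-pairs mean at visit 7** = ρ × SD × E[z | seen].

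| Missing | ρ = 0.6 | ρ = 0.8 |
|---|---|---|
| 10% | 0.6 × 0.089 = 0.053 | 0.8 × 0.089 = 0.071 |
| 20% | 0.6 × 0.200 = 0.120 | 0.8 × 0.200 = 0.160 |

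The range is about 0.05 to 0.16 SD.

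**Step 3: the mixed-model mean.** When visit 7 is the only missing value, the two-visit model's group mean is the observed visit 7 mean + b × (visit 6 mean of all subjects − visit 6 mean of those seen at visit 7), with b the slope of visit 7 on visit 6. At ρ = 0.8 and m = 0.20 the correction is 0.8 × (0 − 0.200) = −0.160, which cancels the bias of +0.160. In simulation at 25 per group the remaining bias is under 0.01 SD, with equal or slightly better precision than the observed-pairs mean.

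**Step 4: sensitivity to the selection assumption.** If a share f of missed visits comes from the worse half, the bias in step 2 is multiplied by (2f − 1).
- f = 1: 0.05 to 0.16 SD
- f = 0.75: multiplier 0.5, so about 0.03 to 0.08 SD
- f = 0.5 (missed visits unrelated to the week-4 result): 0

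**Step 5: effect on the test.** A separate simulation set the true change to zero, with 25 per group, ρ of 0.5 to 0.7, f = 1 and a two-sided 0.05 level. The nominal rate of false significant improvement is 2.5%.

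| Missing | Paired t-test | Mixed-model mean |
|---|---|---|
| 10% | 4.2 to 5.0% | 2.6 to 3.0% |
| 20% | 6.1 to 9.0% | 2.6 to 2.7% |

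**The case against.** The strongest reply is that the plan does not commit to what is criticised. The paired t-test sentence names no visit, 2.15.3 leaves missing-data handling open, and no dropout rate or reason is documented. Withdrawing subjects are asked for a final visit (12.0), and those affected by COVID-19 may return within a year (2.9), so some week-12 values may be recovered. All of that stands. It makes selective loss a risk and not a fact, and it may make the loss smaller. It does not put a subject seen only at week 4 into a visit 7 pair, because the open clause in 2.15.3 leaves the named test as it is.

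Four stronger readings are tempting, and the documents do not support them.

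- A reader might call the test completers-only. It uses observed pairs: a subject who misses visit 7 still counts in a visit 6 test, and the zero-change rule, if applied, brings in subjects with no follow-up at all.
- A reader might infer that the mixed model is barred from within-group use. Section 2.15.5 names one use and does not exclude others.
- A reader might infer a breach of intention-to-treat. The sentence that promises it concerns the primary analysis, and this variable is an additional one. The wider wording in 2.15.3 still argues for using every treated subject's data.
- A reader might infer that a success criterion in 2.15.1 rests on this test. That section does not cite the paired t-test, and its reference value of 4 is the no-change category of the GAIS, not of an FWSS change score. The link is an inference.

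The step 2 figures also sit at the strong end, because they draw every missed visit from the worse half. Step 4 shows how they shrink.

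**Conclusion.** The point holds as a choice of method. For within-group change at visit 7, the plan names the test that discards the week-4 scores of subjects missing week 12, while the same section already fits a model that uses them. Under the stated assumptions the paired t-test overstates improvement by about 0.05 to 0.16 SD, or about half that if three quarters of the missed visits come from the worse half. The model estimate is within 0.01 SD, provided missingness depends on the observed week-4 result. Neither method corrects for missingness that depends on the unseen week-12 result. With no missing data the two point estimates agree. With data missing completely at random, neither is biased and the paired t-test only loses a little precision. The primary criterion, correct identification of pre-treatment images, is not affected. The change is worth making because it costs little.

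**What to change.** In 2.15.5, take each group's mean change at visits 6 and 7, with its 95% confidence interval and two-sided p-value (test against 0), from the mixed model already planned. State the significance level for this test. Keep the paired t-test as a sensitivity analysis in subjects with observed pairs.

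Two related edits are needed.

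- Reconcile the zero-change sentence with the one after it that leaves the changes missing, and say which variable the rule covers. It now refers to the primary efficacy variable, which is image identification and has no change score.
- In 2.15.1, state that no change means 0 for an FWSS change score and that 4 applies only to the GAIS.

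The cost is a few sentences, with no added visits or data. The model's covariance structure, which 2.15.5 does not give, must be stated, and the reported improvement may come out slightly less favourable.
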